#### 2.2.7.1 Primary and Secondary Outcomes

The primary outcome is proportion of participants who sustain at least 5% of baseline weight loss at 18 months. Research assistants will weigh participants in duplicate using a standard

calibrated scale at baseline and 18 months at local clinic sites as in previous and ongoing trials. The primary outcome was selected based on its clinical relevance for patients, providers, and health care systems, as well as patient and stakeholder input. Weight loss of  $\geq 5\%$  of baseline weight is known to confer a reduction in risk of diabetes and other chronic disease. This outcome emphasizes chronic disease prevention by focusing on clinically relevant weight loss. Our patient advisors advocated for this primary outcome because their primary goal for the intervention is to reduce the risk for chronic disease. We will examine three types of secondary outcomes:

**Health behaviors** (dietary intake, physical activity, and sedentary behavior) and psychosocial well being will be collected via phone or online questionnaire at baseline, 6, 12, and 18 months (Aim 2). Dietary intake will be assessed using the gold-standard approach of multiple pass 24-hour recalls in Spanish or English by highly trained and experienced staff, over the phone, at baseline and 18 months. Physical activity and sedentary behavior will be assessed using the interviewer-administered 7-day Physical Activity Recall and a self-report measure of sedentary behavior over the phone at all time points. Participants will complete online questionnaires that we have successfully used in prior trials to assess psychosocial well-being (e.g., EuroQol EQ-5D, PHQ-9 for depression). If needed, a research assistant can help a participant fill out the online questionnaire at an office visit.

**Cardiometabolic risk factors** (blood pressure and waist circumference) measured at baseline and 18 months (Aim 2). Trained research assistants will conduct blood pressure and waist circumference measurement according to standard protocols. Waist circumference will be measured in duplicate at the right iliac crest, in centimeters as per previously published protocols.

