**Table 4. Outcomes, potential effect modifiers and mediators measured at baseline visit (BV), 6, 12, and 18 months (M)**

Outcomes	Measures	Mode	BV	6M	12M	18M
Primary outcome:	Height	In-person	X			
Proportion losing ≥ 5% of baseline weight at 18 months	Weight - standardized methods 	In-person	X			X
Secondary outcomes:	Weight	EHR	Ongoing -> 24 months			
Clinical: Weight change and cardiometabolic risk factors	Waist circumference	In-person	X			X
	Blood pressure- standardized methods 	In-person	X			X
Behavior change:	1. Multiple pass 24-hour diet recall 	Phone	X			X
1. Dietary intake	2. 7-day Physical Activity Recall, 		X	X	X	X
2. Physical activity	3. Sedentary behavior questionnaire 		X	X	X	X
3. Sedentary behavior						
Psychosocial well-being:	1. EuroQol EQ-5D 	Online	X			X
1. Health-related quality of life	2. Obesity-related Problem Scale 					
2. Obesity-specific quality of life	3. Perceived Stress Scale & Nine-item Patient Health Questionnaire (PHQ-9) 					
3. Depressive symptoms	4. PROMIS™ sleep disturbance and Sleep-Related Impairment 					
4. Sleep habits and quality						
Potential modifiers:	1. Age, race/ethnicity, education, employment, occupation, marital status, household size, income, acculturation	In-person	X			
1. Demographics						
2. Technology utilization	2. Adapted from the Pew Hispanic Trust technology use and access survey 	Online	X			
3. Health literacy	3. The newest vital sign 	In-person	X			
Potential mediators:	1. Goals and Relative Weights,  Stunkard silhouettes 	Online	X	X	X	X
1. Outcome expectancy	2. Weight Efficacy Life-Style Questionnaire,  Self-Efficacy for Dietary Change and Exercise 					
2. Self-efficacy	3. Social Support for Diet Change & Exercise 					
3. Social support						
Intervention engagement:	1. Attendance at sessions (in-clinic or online) and tracking of online video viewing	Mobile app	Ongoing			
1. Session attendance	2. Tracking of messages sent/received to coach					
2. Interaction with coach	3. Self-tracking of physical activity, diet, and weight on app or web					
3. Self-tracking						

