### 2.2.9 Statistical Analysis

#### 2.2.9.1 Analytical Plan

Aim 1 and 2: The primary hypothesis that HOMBRE will lead to a greater percentage of Latino men who sustain  $\geq 5\%$  of baseline weight loss through 18 months than the minimal intensity intervention control group will be tested with a generalized linear mixed model.

$$Y = \beta_0 + \beta_1 X + \beta_2 Y_0 + \sum \beta_{4+i} Z_i + \alpha + \gamma + e \quad (1)$$

Let  $Y$  be the outcome of interest for a patient randomized to arm  $X$  (HOMBRE or control). Given the covariate-adaptive randomization, distributions of baseline values on the outcome variable ( $Y_0$ ) and key characteristics ( $Z_i$ ) should be similar between study arms and thus not bias the results. But to the extent they are associated with the outcome, their inclusion in the analysis will account for otherwise unexplained variation and hence increase efficiency.  $\alpha$  and  $\gamma$  are clinic and PCP nested within clinic random effects, and  $e$  is the random error term. Aim 2 examining secondary outcomes at 18 can be evaluated by adapting the same model. The outcome variables in Aim 2 (e.g., cardiometabolic, health behavior, and psychosocial well-being indicators) will be continuous. We will model the change from baseline in each indicator as the outcome  $Y$  and the fixed and random effects will remain the same as described in model (1).

Primary analyses will follow intent to treat principles. We will verify that mixed model-based results are not sensitive to violations of model assumptions with permutation and bootstrap resampling tests. We will document the extent, pattern, and reasons for missing data, and will conduct sensitivity analyses of the impact of missing data on stability of the primary results. For example, we may use weight data up to the point when they are no longer available (e.g., dropouts) or should not be used, and then employ multiple imputation based on a predictive distribution for future weights.

Exploratory Aim 1: Weight loss trajectories using weight data from the EHR will be examined using tests of group-by-time interactions in mixed-effects growth curve model.

$$Y_t = \beta_0 + \beta_1 X + \beta_2 Y_0 + (\beta_3 + \beta_4 X) T + \sum \beta_{4+i} Z_i + \alpha + \gamma + b_0 + b_1 T + \varepsilon \quad (2)$$

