#### 2.2.10 Sample Size and Data interpretation

This trial is powered on the primary outcome of percentage of participants achieving  $\geq 5\%$  weight loss at 18 months. A sample of 212 participants/arm has 80% power to detect a difference of 15 percentage points between the HOMBRE intervention and control at  $\alpha=0.05$  (2-sided), assuming at least 80% retention at 18 months based on our prior trial experiences. We estimated that the percentage of men randomized to the minimal intensity intervention who would maintain clinically significant weight loss at 18 months would be slightly lower than what we observed in a prior trial (39%). Among racial/ethnic minorities, such as Latinos, lower proportions have maintained clinically significant weight loss in the intervention arms (e.g., 18% to 26%). Additionally, other low intensity interventions in primary care have also demonstrated a lower proportion maintaining clinically significant weight loss than what was observed in a prior trial. We chose a 15-point difference in percentage of men achieving  $\geq 5\%$  weight loss at 18 months based on our prior studies and other available literature. Among men randomized to the coach-led intervention in a prior trial, 51% maintained  $\geq 5\%$  weight loss at 24 months (12-point difference between groups). We anticipate a greater difference than observed in our prior trial, given that HOMBRE incorporates facilitated choice or delivery options and the control condition does not. The SHED-IT intervention tested a lower intensity intervention with a higher intensity intervention among Australian men over 12 months and found that 33% and 49% of men randomized to the respective arms maintained clinically significant weight loss (16 point difference).

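### Physical activity and sedentary behavior: the Aim 2 model leaves the 6- and 12-month values out of the 18-month comparison, and no missing-data method is given

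*Combined protocol and SAP*

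**What the plan says.** Section 2.2.7.1 has physical activity and sedentary behavior assessed "over the phone at all time points", and Table 4 marks both at baseline, 6, 12 and 18 months. The Aim 2 hypothesis in section 2.1 is a comparison at 18 months.

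For the analysis, section 2.2.9.1 states "Aim 2 examining secondary outcomes at 18 can be evaluated by adapting the same model". It then makes change from baseline the dependent variable and carries over the fixed and random effects of model (1). Those are arm, baseline value, baseline covariates, clinic, and PCP within clinic.

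A longitudinal model appears only for weight: "Weight loss trajectories using weight data from the EHR will be examined using tests of group-by-time interactions in mixed-effects growth curve model" (model 2).

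On missing data, the plan will document extent, pattern and reasons, and "will conduct sensitivity analyses of the impact of missing data on stability of the primary results". The one technique it mentions is multiple imputation of future weights, offered as something the team may do.

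The psychosocial schedule is unclear. The group sentence in section 2.2.7.1 reads "psychosocial well being will be collected via phone or online questionnaire at baseline, 6, 12, and 18 months", but Table 4 marks those measures at baseline and 18 months only. The same sentence also covers diet, which is then collected "by highly trained and experienced staff, over the phone, at baseline and 18 months", so it may be a loose summary.

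**The concern.** Two outcomes are measured three times after randomization and analyzed once. Model (1) takes one value per man, so a man who gave 6- and 12-month data but missed month 18 adds nothing to the comparison. The plan does not state a complete-case rule, but that is what the model does.

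Two things are at stake. One is a modest loss of precision. The other is bias, if leaving before month 18 is related to earlier results differently in the two arms. Men know their assignment (section 2.2.3), and coach contact differs by arm (sections 2.2.5.3 and 2.2.5.4), so this cannot be excluded. The documents describe no dropout mechanism either way.

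**Working it through.** **1. Scope.** Text and Table 4 agree on four time points for physical activity and sedentary behavior. Diet, blood pressure and waist have no interim values to use. The psychosocial measures qualify only if the 6- and 12-month collection is real.

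**2. Can the interim values enter?** Model (1) has no visit term, no arm-by-visit term and no participant effect. With its terms carried over unchanged, they cannot. The mediation analysis does not name these two behaviors either.

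**3. The plan's own figure.** Section 2.2.10 gives 212 per arm and 80% power for 15 points, "assuming at least 80% retention at 18 months based on our prior trial experiences". Evaluable: 212 × 0.80 = 169.6 per arm. With an assumed 35% vs 50%, power is 80.1%. The figure reproduces and is not in dispute. No power is stated for the two behaviors.

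**4. Assumed inputs.** Outcomes in SD units, scored so that higher is better. Missing at 18 months: 10-20%, spanning the retention in sections 2.2.8 and 2.2.10 (at least 80% planned; 82%-92% and 85% in earlier trials). That retention may not carry over to phone-collected outcomes. Mid case: baseline-to-follow-up correlation b = 0.45, correlation between follow-ups f = 0.65, and two-thirds of leavers with 6- and 12-month data. None of these correlations or shares is in the documents.

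**5. Precision under random dropout.**
- Partial correlation given baseline: r = (f − b²)/(1 − b²) = (0.65 − 0.2025)/0.7975 = 0.561.
- Share of 18-month variance explained by the two interim values: R² = 2r²/(1 + r) = 0.6296/1.561 = 0.403.
- Let c be the share with an 18-month value and m the share with interim values. Variance ratio (18-month only ÷ all visits) = (1/c) / [(1 − R²)/c + R²/m].
- At 20% missing, c = 0.80 and m = 0.80 + 0.20 × 2/3 = 0.933. Ratio = 1.25/(0.597/0.80 + 0.403/0.933) = 1.25/1.178 = 1.06.
- At 15% and 10% missing the same formula gives 1.04 and 1.03.

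Simulation (3,000 trials per setting, b/f from 0.4/0.5 to 0.5/0.8) gave 2-6% extra variance at 10% missing, 2-8% at 15% and 4-9% at 20%. Varying the interim-data share from one-half to all leavers widens this to 2-15%.

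In the mid case at 20% missing, 170 men per arm act like 170 × 1.06 ≈ 180. A comparison with 80% power would have Φ(2.8016 × √1.06 − 1.96) = 0.822.

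**6. Bias.** True effect 0.20 SD, 212 per arm, mid-case correlations. Estimator A is baseline-adjusted 18-month change among men with an 18-month value. Estimator B is the likelihood estimate that also uses months 6 and 12.

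Random dropout: A is unbiased. Dropout depending on month 12 in the same way in both arms (slopes 0.5 and 1.0): A is off by 0 to −0.010 SD.

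Dropout depending on month 12 in HOMBRE only, bias of A in SD:

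| Log-odds slope per SD | 10% missing | 15% missing | 20% missing |
|---|---|---|---|
| 0.3 | 0.014 | 0.021 | 0.027 |
| 0.5 | 0.023 | 0.033 | 0.043 |
| 1.0 | 0.041 | 0.060 | 0.078 |

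B leaves about 0.005 to 0.022 SD across these cells. The remainder arises because a third of leavers depart according to a month-12 value that was never recorded. If early leavers instead go at random and only later leavers depend on month 12 (20% missing, slope 1.0), A is off by 0.057 SD. B is then off by 0.000, as is multiple imputation by arm.

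**7. Scale.** The standard error of A is √[2(1 − b²)/n]. At 15% missing, n = 180.2 and it is √(2 × 0.7975/180.2) = 0.094 SD. At 20%, n = 169.6 and it is 0.097 SD. A bias of 0.033 SD at 15% is about a third of a standard error (0.033/0.094 = 0.35); the worst cell is 0.078/0.097 = 0.80.

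**The case against.** An 18-month change adjusted for baseline answers the Aim 2 question, so this is not an error or a contradiction. That is right; the proposal keeps the same contrast and changes only which data inform it.

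The missing-data paragraph falls under the joint Aim 1 and 2 text, and imputation of weight is introduced as an example, so it might extend to Aim 2. The reference to primary results and the optional wording favor the narrow reading. Documenting missingness is not a method for handling it.

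The harmful scenario is unproven. Both programs run 12 months, so scheduled coach contact ends before the window in which an observed month-12 value could drive dropout. The plan also re-contacts men who miss visits (section 2.2.8) and reviews attrition by arm (Table 5). These points lower the priority. Monitoring could reveal differential attrition but would not correct the estimate.

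The gain may be very small. With b = f = 0.3, r = 0.21/0.91 = 0.231 and R² = 0.087. At 20% missing with two-thirds interim data, the extra variance is then only about 1%.

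Lastly, the missing-data gap applies equally to diet, blood pressure and waist. That also stands: there are no interim values to exploit there, but the SAP should still state its assumption.

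**Conclusion.** The point holds as a low-cost improvement to consider. As written, the 6- and 12-month values of physical activity and sedentary behavior cannot inform the 18-month contrast, and no missing-data method covers these outcomes.

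With random or arm-neutral dropout, the loss is a few percent of precision. A material bias needs dropout that follows interim results differently by arm: up to 0.078 SD in the one-arm scenarios above. A harsher case, with opposite directions in the two arms, 20% missing, slopes 0.5-1.0 and correlations 0.3-0.7, gives about 0.05 to 0.13 SD. Neither mechanism is documented, and every size rests on assumed correlations and an assumed share of leavers with interim data. Interim values cannot repair dropout driven by unobserved results.

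**What to change.** For physical activity and sedentary behavior, specify one of these in the SAP before arm-level results are seen:

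- A linear mixed model for repeated measures on the 6-, 12- and 18-month values, with arm by visit, baseline by visit, unstructured within-man covariance, and the existing covariates and clinic/PCP terms. Report the 18-month arm contrast.
- Model (1) at 18 months after multiple imputation by arm, with the 6- and 12-month values in the imputation model.

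State the missing-at-random assumption behind the choice. Keep the current model for diet, blood pressure and waist, and say how missing 18-month values are treated there. Reconcile section 2.2.7.1 with Table 4 on the psychosocial schedule, and the group sentence on diet. Apply the new method to psychosocial outcomes only if they are in fact collected at 6 and 12 months.

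The cost is SAP wording and minor programming. No new data are needed, and the hypothesis and 18-month contrast do not change.

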### 2.2.5.2 Self-monitoring

Participants in both arms will receive a digital scale to self-monitor weight, a wearable fitness tracker to self-monitor physical activity, and will be asked to use MyFitnessPal web or Smartphone application to track dietary intake. In pre-testing the Latino Patient Advisory Board concluded the application had high acceptability based on the language, ease of entering cultural foods, opportunities for social networking, and availability both on the phone and personal computer. We will help participants to set up the activity monitor at the baseline visit to ensure that these data are automatically and wirelessly synced with the self-monitoring application (MyFitnessPal) with minimal participant action needed except for wearing the device. MyFitnessPal is a free web- and mobile-based (Android, iOS, and Windows compatible) tracking application available in Spanish and English. Self-monitored data collected through the MyFitnessPal application will be used by the lifestyle coach to provide individualized feedback and guidance tailored for Latino men. In addition, self-monitoring data (e.g., self-monitoring frequency) will be used to assess intervention participants' engagement and adherence.

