**Body Weight from the EHR up to 24 months post-randomization.** We will abstract weight measurements from the EHR 3 months prior to randomization and up to 24 months post-randomization to examine trajectories of weight loss over time. We examined the feasibility of this approach by comparing data on researcher-measured weights and EHR-weights in two prior behavioral lifestyle intervention trials. Using data from two prior trials we observed that participants had a sufficient number of weight measurements in the EHR and there was excellent agreement between researcher-measured weights and weight obtained in the EHR.

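### The plan gives no primary handling for a missing 18-month weight, and its optional imputation is not explicitly tied to the EHR weights that are already being collected.

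*Combined protocol and SAP*

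**What the plan says.** Section 2.2.9.1 tests the primary hypothesis with model (1), a generalized linear mixed model for reaching at least 5% loss at 18 months. It has one outcome per man, baseline covariates, and random effects for clinic and for PCP within clinic. "Primary analyses will follow intent to treat principles". For missing data the section commits to documenting extent, pattern and reasons, and the team "will conduct sensitivity analyses of the impact of missing data on stability of the primary results". The one method named is an example: "we may use weight data up to the point when they are no longer available", followed by multiple imputation. The section does not say which weights these are, or when weights should not be used.

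Study staff weigh men on a "calibrated scale at baseline and 18 months at local clinic sites as in previous and ongoing trials" (section 2.2.7.1), and Table 4 shows no study weight in between. The same section adds: "We will abstract weight measurements from the EHR 3 months prior to randomization and up to 24 months post-randomization". The only analysis in section 2.2.9.1 that names these weights is Exploratory Aim 1: "Weight loss trajectories using weight data from the EHR will be examined using tests of group-by-time interactions". The Discussion describes EHR follow-up over 24 months as a supplement to the two study visits. Section 2.2.10 assumes at least 80% retention at 18 months.

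**The concern.** A man who misses the 18-month visit has no post-baseline study weight. Model (1) has no within-person term and takes no intermediate weights, so nothing in it can carry him. Unless a rule is added he drops out of the fit, and the primary result becomes a comparison of men who came back. Intent to treat settles which arm a man is counted in; it does not say what value he contributes when the outcome is missing.

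Sensitivity analyses test a primary result but do not define it. If the rule is chosen after the data are seen, the primary estimate can depend on that choice. Meanwhile the trial already collects serial weights for both arms that bear on the missing values, and the primary analysis makes no stated use of them.

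**Working it through.** **1. The plan's own figure.** Section 2.2.10 gives 212 per arm, 80% power, a 15-point difference, two-sided 0.05 and 80% retention. It gives no control rate, only that it is slightly below 39%; we assume 33% to 39%. The pooled two-proportion formula without continuity correction at 34% vs 49% gives 169 evaluable per arm, and 169/0.80 = 211.25, rounded up to 212. Across 33% to 39% the result is 209 to 217. The stated figure reproduces.

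**2. Men without a primary outcome.** 0.20 × 212 = 42.4, so up to about 42 per arm.

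**3. Completers only, no true effect.** Our assumptions: 40% true success in both arms; missing men succeed at rate m; retention r differs by arm.

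Completer success rate = (0.40 − (1 − r) × m) / r

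With m = 0.15 and r = 0.82: (0.40 − 0.18 × 0.15)/0.82 = 0.373/0.82 = 45.49%. With r = 0.85, 0.88 and 0.92 the rate is 44.41%, 43.41% and 42.17%. Rejection is two-sided at nominal 5%, by normal approximation (pooled SE for the test, unpooled SE for its distribution), with 212 × r men per arm.

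| Retention HOMBRE/control | m = 15%: bias, rejection | m = 30%: bias, rejection |
|---|---|---|
| equal | 0, 5.0% | 0, 5.0% |
| 82%/85% | +1.1 points, 5.5% | +0.4 points, 5.1% |
| 82%/88% | +2.1 points, 6.8% | +0.8 points, 5.3% |
| 82%/92% | +3.3 points, 9.8% | +1.3 points, 5.8% |

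The signs reverse if control loses more men. The 82% and 92% are a range across earlier trials in section 2.2.8, used here as an extreme gap between arms.

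**4. Dropout that depends on outcome identically in both arms.** Assume a true 50% vs 35%, with 95% of successes and 69% of failures retained.

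- HOMBRE: 0.475/(0.475 + 0.345) = 57.93%
- Control: 0.3325/(0.3325 + 0.4485) = 42.57%

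The difference is 15.4 points against a true 15. The odds ratio is 1.857, equal to the true value.

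**5. Dropout explained by a baseline covariate.** Simulation with no true effect, 18%/8% missing, and one covariate correlated 0.3 or 0.5 with weight change. Unadjusted completers are biased by about 1.2 or 2.1 points. The bias essentially vanishes once completers are adjusted for that covariate, as model (1) does for any covariate it includes. Imputing from baseline data alone therefore adds little.

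**6. Dropout driven by weight change itself.** Same 18%/8%, missing men succeeding at 15%, completers' bias 3.3 points. We assume normally distributed percent change with SD 7 and an EHR weight for 80% of weighed men. Without an EHR weight for any missing man, imputation leaves all of the bias. Otherwise the share remaining is:

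| Missing men with an EHR weight | correlation 0.5 | 0.7 | 0.9 |
|---|---|---|---|
| 25% | 0.94 | 0.86 | 0.76 |
| 50% | 0.87 | 0.73 | 0.53 |
| 75% | 0.81 | 0.61 | 0.35 |

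The correlation is between the EHR weight's change and the 18-month change. Multiplied by 3.3 points, this leaves 2.5 to 3.1, 1.8 to 2.9 and 1.2 to 2.7 points.

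**The case against.** The plan is not silent. It commits to documenting missingness and to sensitivity analyses, Table 5 promises attrition by arm, and section 2.2.8 has staff contact men who miss a visit. Talk of weights up to a cut-off and of future weights implies a series, and the EHR is the only serial weight stream listed as an outcome, so it is the natural reading. The bias is small unless retention differs widely between arms, and any reasoned rule, once stated, would close the gap.

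Most of this stands. A reader might infer that the imputation source is wholly open, including home weights: "Participants in both arms will receive a digital scale to self-monitor weight", and Table 4 lists "Self-tracking of physical activity, diet, and weight on app or web". The documents do not support that reading. Section 2.2.5.2 assigns self-monitoring data to coach feedback and to assessing engagement and adherence, and Table 4 files them under engagement. The gap is narrower: the link to EHR weights is left to the reader, and the imputation is optional and outside the primary analysis. It is also fair that imputation is one acceptable rule among several. We prefer it because it uses information already collected on the men who would otherwise be dropped.

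**Conclusion.** The point holds in limited form. That no primary handling is stated can be read directly from section 2.2.9.1, and we hold it with high confidence. That the analysis would use completers only is our inference from the form of model (1).

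The size depends on retention by arm and on success among missing men, neither of which the documents give. Bias is nil or small under similar dropout or dropout explained by model covariates. With 15% success among missing men it is about 1 to 2 points for gaps of 3 to 6 points in retention. The 3.3 points and 9.8% rejection need both a 10-point gap and that low success rate.

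Three stronger readings go too far. The intent-to-treat statement is incomplete, but nothing in the plan contradicts it. The primary result cannot be called biased in advance. And the allowance for 20% loss neither shows that a completers' analysis was intended nor makes 212 per arm wrong.

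**What to change.** In section 2.2.9.1, state that the primary analysis includes all randomised men. Multiply impute the missing 18-month weight, separately by arm and on the continuous scale, from baseline covariates and all post-randomisation EHR weights, adding the 6- and 12-month measures in Table 4 where available. Then derive 5% loss and fit model (1). Replace the optional wording with a commitment to two sensitivity analyses: completers only, and a delta-adjusted imputation in which missing men do worse. Report by arm how many men lack the study weight and how many of those have an EHR weight.

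The cost is SAP wording and some programming. No new visits or data are needed, and the sample size stays at 212 per arm. The downside is reliance on routine-care weights, which may be sparse for men who miss the visit; the Discussion itself notes that men may use healthcare infrequently. Against that, section 2.2.7.1 reports enough EHR weights and excellent agreement with researcher-measured weights in two prior trials, though this may not carry over to men who drop out. The 6- and 12-month measures may be missing for the same men. Because EHR weights remove only part of the bias when dropout depends on weight change, the delta-adjusted analysis is needed alongside.
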